A Hybrid Type 2 Trial of Trauma-Focused Cognitive Behavioral Therapy and a Pragmatic Individual-Level Implementation Strategy

NCT04451161

Unique Protocol ID: STUDY00008401

Secondary IDs: 1R01MH119148-01A1 [U.S. NIH Grant/Contract Award Number]

3/5/2025

Study Protocol and Statistical Analysis Plan

Table of Contents

SECTION ONE: INTRODUCTION	2
SECTION TWO: INTERVENTION.....	5
SECTION THREE: RECRUITMENT AND CONSENTING	11
SECTION FOUR: MEASURES AND DATA COLLECTION	15
SECTION FIVE: QUALITATIVE DATA COLLECTION AND ANALYSIS: RECORDING AND CODING.....	21
SECTION SIX: DATA ANALYSIS PLAN	23

SECTION ONE: INTRODUCTION

1. Project Overview

The University of Washington School Mental Health Assessment, Research, and Training (SMART) Center, under the leadership of Principal Investigators [name] Ph.D. (UW) and [name] (University of Minnesota), received funding from the National Institutes of Health to conduct a 5-year research study. The study, “A Hybrid Type 2 Trial of Trauma-Focused Cognitive Behavioral Therapy and a Pragmatic Individual-Level Implementation Strategy” is referred to simply as BASIS and took place in multiple states across the nation. The BASIS study is a randomized controlled clinical trial designed to simultaneously test the effectiveness of TF-CBT in schools on student outcomes (e.g., trauma symptoms) and the impact of BASIS on implementation outcomes (e.g., adoption of TF-CBT). This study has been reviewed and approved by the University of Washington Human Subjects Review Board.

2. STUDY PURPOSE

[figure not shown]
Despite serving as the most common setting where youth receive mental health services, schools are confronted with two gaps that prevent youth from accessing evidence-based care: (1) an access gap characterized by the limited availability of high-quality trauma treatments; and (2) an implementation gap consisting of insufficient adoption, fidelity, and sustainment of EBTs. To address both gaps, this project proposes a hybrid

type 2 effectiveness-implementation trial simultaneously examining TF-CBT effectiveness in the education sector and the impact of the BASIS implementation strategy for promoting TF-CBT use. TF-CBT has robust support demonstrated by a variety of efficacy studies, and BASIS has support as a feasible and appropriate implementation strategy. Consistent with NIMH's experimental therapeutics approach to intervention evaluation, this project examined the mechanisms through which TF-CBT influenced clinical outcomes, as well as the mechanisms through which BASIS influences implementation outcomes.

3. STUDY DESIGN

We conducted a hybrid type 2 effectiveness-implementation randomized trial. There was single provider from each participating school, for first cohort, then more than one provider after the first year (n=158) were randomized to BASIS plus TF-CBT (BASIS+TF-CBT), Attention Control plus TF-CBT (AC+TF-CBT), or Resource Efficient Treatment Intervention (RETI). **Aim 1** evaluated the main effects of TF-CBT on proximal mechanisms and clinical child outcomes, as well as test intervention mechanisms as mediators, moderators, and evaluate the cost-effectiveness of the intervention. **Aim 2** evaluated the main effects of BASIS on its mechanism of change and provider implementation outcomes, as well as test implementation mechanisms as mediators, moderators, and evaluated the cost-effectiveness of BASIS strategy. In addition, sequential mixed-methods data collection will explore how mechanisms are linked to implementation outcomes for "hypothesis defying residuals" (i.e., providers whose attitudes, subjective norms, and self-efficacy surrounding Evidence-Based Treatment (EBT) implementation are inconsistent with their documented implementation behaviors).

Project Timeline Overview (see Section 2.7 of Clinical Trials Information for fully detailed timeline)	Months 0-6 (Dec 2019- May 2020)	Months 6-12 (Jun 2020- Nov 2020)	Months 12-18 (Dec 2020- May 2021)	Months 18-24 (Jun 2021- Nov 2021)	Months 24-30 (Dec 2021- May 2022)	Months 30-36 (Jun 2022- Nov 2022)	Months 36-42 (Dec 2022- May 2023)	Months 42-48 (Jun 2023- Nov 2023)	Months 48-54 (Dec 2023- May 2024)	Months 54-60 (Jun 2024- Nov 2024)
Activities										
Clinician recruitment (n=120)		X		X		X				
Student recruitment (n=480)		X	X	X	X	X	X			
BASIS or Attention Control delivery		X		X		X				
TF-CBT or TAU delivery	X	X	X	X	X	X	X			
Clinician data collection	X	X	X	X	X	X	X	X		
Student data collection	X	X	X	X	X	X	X			
Aim 1 & 2 analyses							X	X		
Aim 1 & 2 manuscripts & dissemination							X	X	X	

SECTION TWO: INTERVENTION

1. CONDITIONS OVERVIEW

Providers were randomized to one of two TF-CBT conditions or a RETI (Resource Efficient Trauma Intervention) condition. Those randomized to TF-CBT will receive either BASIS + TF-CBT or Attention control (AC) + TF-CBT. Both BASIS and AC bookend the TF-CBT 3-day training and will be followed by an online booster session. TF-CBT gold-standard training and 6 months of follow-up consultation were delivered by [name], [name], and [name].

Three Research Groups

BASIS plus TF-CBT (B + TF-CBT)

Providers in this research condition received the BASIS intervention prior to and post TF-CBT training.

Attention Control plus TF-CBT (AC + TF-CBT)

Providers in this research condition received attention control prior to and post TF-CBT training.

Resource-Efficient Trauma Intervention (RETI)

Providers in this research group received a half-day training and handout in RETI practices.

Clinical Interventions

RETI

Resource-Efficient Trauma Intervention (RETI) can be described as scaffold treatment-as-usual. It is a less prescriptive and resource-intensive intervention. It includes four core components – initial assessment, psychoeducation, social connection, and planning – which involve identifying which students have trauma exposure, connecting them to a practitioner who provides psychoeducation and social support, and the development of a support plan. This second approach provides school service providers with greater flexibility and autonomy but has been tested less extensively.

TF-CBT

TF-CBT was selected based on its established evidence and the stated need of participating districts to address student trauma and increasing concerns about student safety. TF-CBT is a 12-16 session intervention for students aged 3 to 18 years with trauma-exposure and related mental health sequelae. TF-CBT includes individual sessions for the youth, individual sessions for parents, and conjoint sessions that include involvement. The first third of TF-CBT focuses on psychoeducation and developing coping skills to reduce trauma-

related distress (e.g., cognitive coping). The middle third focuses on cognitive processing of trauma-related cognitions and beliefs and on exposure- both imaginal exposure to traumatic events as well as situational exposure to trauma-related reminders likely to be overgeneralized (e.g., fear of the dark). The final third continues these components and focuses on the future, including enhancing future safety and preventing relapse. All school mental health providers will be required to complete TF-CBT online training (providers will be compensated) a week prior to participating in a standard 2-day training delivered by certified TF-CBT trainer, [name], who will be blind to condition. He will also provide biweekly group consultation to providers within the BASIS or AC condition to avoid contamination.

TF-CBT is a short-term treatment typically provided in 12 to 14 weekly sessions. Most sessions last approximately 45-50 minutes. Each individual session is designed to build the therapeutic relationship while providing education, skills, and a safe environment in which to address and process traumatic memories.

TF-CBT is an evidence-based treatment that helps children from elementary to high school to address the negative effects of trauma and promote greater emotion and behavior regulation, including processing their traumatic memories, overcoming problematic thoughts and behaviors, and developing effective coping and interpersonal skills. It also includes a treatment component for parents or other caregivers. Parents can learn skills related to stress management, positive parenting, behavior management, and effective communication.

When possible, joint parent-child sessions are held to help parents and children practice and use the skills they learned and to assist the children in sharing their trauma narratives. Components of the TF-CBT can be summarized by the word “PRACTICE”:

- **P** - Psychoeducation and parenting skills— Discussing and teaching about emotional and behavioral reactions to trauma and other emotion-provoking situations as well as skills training for parents in positive parenting, child behavior management strategies and effective communication
- **R** - Relaxation techniques—Teaching relaxation methods, such as focused breathing, progressive muscle relaxation, and visual imagery, which may benefit the parent as well
- **A** - Affective expression and regulation—Helping the child and parent manage their emotional reactions to reminders of the abuse, improve their ability to identify and express emotions, and participate in self-soothing activities
- **C** - Cognitive coping and processing—Helping the child and parent understand the connection between thoughts, feelings, and behaviors and exploring and correcting inaccurate and/or unhelpful attributions related to everyday events
- **T** - Trauma narration and processing—Conducting gradual exposure exercises, including verbal, written, and/or other creative recounting of abusive events, and processing inaccurate and/or unhelpful thoughts about the abuse

- **I** - In vivo exposure—Gradual exposure to trauma reminders in the child’s environment (e.g., darkness, the setting where the trauma occurred), so the child learns to control his or her own emotional reactions
- **C** - Conjoint parent/child sessions—Family work to enhance communication and create opportunities for therapeutic discussion regarding the abuse and for the child to share his/her trauma narration
- **E** - Enhancing personal safety and future growth— Education and training on personal safety skills, interpersonal relationships, and healthy sexuality and encouragement in the use of new skills in managing future stressors and trauma reminders.

Example web resources with overview of the research supporting TF-CBT:

- <http://www.episcenter.psu.edu/newvpp/tfcbt/research>
- <https://www.cebc4cw.org/program/trauma-focused-cognitive-behavioral-therapy/>

Pre-Implementation Strategy: BASIS

Beliefs and Attitudes for Successful Implementation in Schools (BASIS) is a brief, group-based pre- implementation strategy that is designed to augment standard evidence-based treatment (EBT) training and consultation for school-based clinicians and is designed to be generalizable across different mental health EBTs and service delivery contexts. It targets individual-level clinician factors associated with behavior change – clinician attitudes, subjective norms, self-efficacy, maintenance self-efficacy, intentions to implement an intervention– using strategies targeting motivation and decision-making.

BASIS is group-based and interactive, with a pre-training session (~3 hours) delivered prior to TF-CBT training, a post-training session (~45 mins) delivered immediately after training, and an online booster 30-days post-training. With training from [name], BASIS will be delivered by [name], LICSW Social Worker with experience consulting with schools and implementing EBTS.

Box 1. BASIS Components

Motivational Components (TPB Mechanisms)

1. Strategic Education (Attitudes)

- a. Connecting EBP to student success
- b. Problems with implementing non-EBPs
- c. Addressing common myths about EBPs
- d. Evaluating evidence for practices
- e. Promoting understanding of fidelity for EBP

2. Social Influence (Subjective Norms)

- a. Providing normative information
- b. Testimonials from experts
- c. Testimonials from similar others
- d. Evoking public commitments

3. Motivational Interviewing (Self-Efficacy)

- a. Professional values clarification activity
- b. Pros & cons activity to elicit change talk
- c. Anticipating implementation barriers
- d. Values-directed goal setting
- e. "Ruler questions" (e.g., how confident are you?)

Volitional Components (HAPA Mechanism)

4. Action Planning and Problem-Solving Planning

(Maintenance Self-Efficacy)

- a. Action planning to initiate implementation
- b. Problem-solving planning to overcome barriers

BASIS Motivational Component 1: Strategic education about EBT and intervention fidelity to improve attitudes. To influence providers' attitudes toward EBT, BASIS incorporates strategic education that focuses on increasing belief about the benefits of EBT for them and the youth they serve.

BASIS Motivational Component 2: Social influence techniques to alter perception of subject norms. Evidence-based social influence strategies consist of two broad categories: 1) social proofing messages that use data or testimonial to describe the behavior or attitudes of others, and 2) strategies to induce cognitive dissonance.

BASIS Motivational Component 3: Motivational Interviewing (MI) to enhance self-efficacy.

BASIS Volitional Components: Action planning and problem-solving planning to promote maintenance self-efficacy. Problem-solving generates solutions in response to both situational and internal (e.g., cognitive) barriers to facilitate follow through with the action plan. In combination, action planning and problem-solving planning increase the likelihood that implementation intentions translate into behavior change.

BASIS Structure:

- The BASIS pre-training session targets attitudes, subjective norms, and self-efficacy. The pre-training session is intended to help participants a) link EBT delivery to improve outcomes for students who are otherwise unable to access care, b) recognize common cognitive shortcuts that leave individuals to adopting non-EBT, c) debunk common myths about EBTs, d) identify characteristics of EBT, standards for quality of scientific evidence, and resources for determining the scientific evidence of available program, and e) deepen understanding of the critical role of fidelity.
- The BASIS post-training session includes volitional strategies to maintain implementation intentions and facilitate actual enactment of behavior change. Specifically, providers will be supported to develop action plans and problem-solving plans. Providers will be provided with an action planning template to detail precisely what TF-CBT complements, how, with whom, where/when, and the environmental cues and resources needed to initiate delivery of TF-CBT with fidelity.
- The BASIS online booster was delivered 30-days post-training, a time point indicated by our prior research when providers' implementation intentions and behaviors may weaken. The aim of the BASIS booster is to provide individualized content to providers to either increase intention to implement or maintain self-efficacy to implement the EBT, depending on whether providers have initiated TF-CBT implementation.

1. AC + TF-CBT

Providers randomly assigned to AC + TF-CBT will receive a 3-hour pre-training, 45-min post-training session, and an online booster 30-days post training to mirror the duration of BASIS and provide control providers with comparable amounts of attention. The in-person or virtual components of AC will be delivered by the same facilitator as BASIS ([name]) to control for facilitator effects. Content will be didactic, as in typical training for school mental health providers. The AC pre-training will provide content on the definition of Evidence-Based Treatment (EBT), how EBTs are established, why providers should use EBTs, clinical outcomes associated with different EBTs, and defining different dimensions of fidelity. The post-training session will involve having control providers reflect on TF-CBT, its core components, and discuss the outcomes associated with TF-CBT. The AC booster will prompt providers to reflect on and describe TF-CBT and identify and define each of its core components. The AC condition thus controls for dose, information provided, and interventionist effect.

1.2 Pre-Training Activities for internal teams:

2-4 Months Before Training (Ordinal Tasks must be completed in order; assumes dates have been set)

- Collect school demographics information

- Send Provider Baseline, give 1-2 weeks for completion
- Complete and ship goodie bags to district administrators
- Randomize Providers based on baseline and demographics information

1 Months Before Training

- Send Self-Paced Training link for those who are in TF-CBT
- Send out Zoom link and training calendar invites to /trainers
- Send reminder email for SPT link and reiterating dates for trainings

2 Weeks Before Training

- Check SPT completion rates, send reminders as needed
- Check-in with trainers
- Send out Zoom link and training calendar invites to participants/trainers

1 Week Before Training

- Reminder sent, links for training included
- T1 sent for completion
- Send YouTube training videos for research activities
- Friday before training – check for SPT completion and send reminders as needed

Training Day

- Send out Self-Paced Training gift cards for TF-CBT participants
- Check all T1 completion, send reminders to those who did not complete
- During training first 5 minutes: call on those who have not completed T1 to take time to complete T1
- Following training: send out T2 surveys to be completed by following morning for TF-CBT
- Following training: send out T5 surveys, payment, and relevant information for RETI participants

RANDOMIZATION

Providers and student random assignments occurred at the school level, with one provider per school recruited for the first year, and multiple people per school building was recruited for year two and three. We use this strategy to minimize analytic difficulties associated with reliably partitioning school and provider variance with small numbers of providers per school. Providers and TF-CBT trainers/consultants would be blinded to their BASIS condition assignment. To ensure comparability of conditions at baseline, minimize potential confounding, and maximize accuracy of effect estimates, we used a blocked randomization design. Schools were first blocked by state (WA, MN, IN, KY, WI, VT, PA, AZ, and MD) and district. We collected baseline provider data on implementation intentions and TPB and HAPA mechanisms (e.g., attitudes, norms, self-efficacy), identify matched pairs using these variables, and randomly assign providers within pairs to condition. Students were placed into TF-CBT or RETI based on the condition into which their school's existing SMH provider was randomized.

SECTION THREE: RECRUITMENT AND CONSENTING

SCHOOL DISTRICT

Participating schools (n=133) are located across multiple states. Schools are situated in diverse settings, including rural (n=1), suburban (n=2), and urban (n=2) regions and have total enrollments of 9,658 - 37,971 students. Student populations are diverse overall, with a mean of 44% of students identifying as racial/ethnic minorities (range 30% to 60%)

PROVIDER

Provider participants include 191 school mental health providers who were consented and randomized, but only 146 completed the BASIS+TF-CBT, AC+TF-CBT, RETI training to continue in the study. Provider recruitment across all three waves will occur with the assistance of district administrators. Principals will provide us with the email addresses of school mental health providers for recruitment.

1. Provider SCREENING CRITERIA

In order of preference:

1. Dedicated mental health providers that have regular individual psychotherapy sessions

- a. The school employed favorable over CBO (Community Based Organization), but CBO is a close second
2. People who devote some, but not all of their time to direct service delivery with students (e.g., pulling kids out and doing interventions), like...
 - a. School Social Worker;
 - b. School Counselors IF they are doing direct care with students
3. Least Preferred: Behavioral Support Specialist who are dealing more the externalizing end of the spectrum

Clinician Inclusion Criteria:

1. Must provide school-based services in a participating district
2. Have no previously received formal training in TF-CBT
3. Are not actively receiving support to implement another intervention
4. Willingness to dedicate a year to participate in the project
5. Are open to become randomly assigned to one of the three conditions

Clinician Exclusion Criteria

- Are not administering direct care to students
- Previously received formal training in TF-CBT
- High school guidance counselors unless their role involves some direct service delivery of mental health services

Provider Screening Guidelines + Screener Survey:

Please indicate the types of training in Trauma-Focused Cognitive Behavioral Therapy (TF-CBT) you have received. (Please check all that apply.)

- Completed the 2-day intensive live, in-person or virtual TF-CBT training. NOT ELIGIBLE
- Completed the 3-day intensive live, in-person or virtual CBT Plus training (with one day on TF-CBT). NOT ELIGIBLE

- Completed one day or less of live, in-person or virtual training. ELIGIBLE
- Completed a fully dedicated, graduate level course on TF-CBT. NOT ELIGIBLE
- Completed (or partially completed) the self-paced, online training course, TF-CBT Web. ELIGIBLE
- Completed (or partially completed) the self-paced, online TF-CBT for childhood grief training course, CTG Web. ELIGIBLE
- Completed training in another evidence-based treatment(s) for children and adolescents impacted by trauma: ELIGIBLE
 - EMDR
 - CBITS
 - Prolonged Exposure
 - Cognitive Processing Therapy
 - Other, Please specify: _____
 - Read the 2015 *Child Sexual Abuse: A Primer for Treating Children, Adolescents, and Their Nonoffending Parents* by Esther Deblinger, Anthony P. Mannarino, and Judith A. Cohen. ELIGIBLE
 - Read the 2016 *Trauma-Focused CBT for Children and Adolescents: Treatment Applications* by Judith A. Cohen, Anthony P. Mannarino, and Esther Deblinger. ELIGIBLE
 - Read the first (2006) or second (2017) edition of *Treating Trauma and Traumatic Grief in Children and Adolescents* by Judith A. Cohen, Anthony P. Mannarino, and Esther Deblinger. ELIGIBLE
 - Other, Please specify: _____ CONTINUE TO CONSENT, BUT STUDY STAFF NEEDS TO VERIFY BEFORE RANDOMIZATION

STUDENT/CAREGIVER

Youth participants (n=101), recruited by school mental health providers via their standard referral pathways (e.g., teacher - or self-referral; screening).

Inclusion

- Must meet TF-CBT eligibility criteria, including:

[figure not shown]
- Be within the TF-CBT developmental range (grades 3-12)
- Have traumatic event exposure
- Significant post-traumatic stress symptoms as indicated by a CPSS-V score ≥ 21

Exclusion

- Students with intellectual impairments or those who are not trauma exposed will be excluded
- Students (and caregivers at this time) must be English speaking

SCREENING CRITERIA

[figure not shown]
Providers will screen new cases for symptoms of trauma using a Trauma Screen (TS) and the Children PTSD Symptom Scale DSM-V (CPSS-5.) Once students are identified, providers will ask caregivers whether they are open to being contacted by the research team.

CONSENT/ASSENT AND ADMINISTRATION PROCESS

For caregivers who agree, contact information will be related to the team, who will follow up by phone to describe the research project, estimated time to participate, participant compensation, and obtain oral consent (a consent form will subsequently be mailed to

participants). For caregivers who consent, research staff will explain the study to students, answer questions, and obtain assent for participation. The procedures we used are based on prior collaboration with students on how best to communicate and approach obtaining assent.

SECTION FOUR: MEASURES AND DATA COLLECTION

[figure not shown]

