	Aim 1b: Evaluate main effects on child mental health outcomes (symptoms of PTSD, depression, anxiety) and test intervention mechanisms via a mediational model.	Multilevel Model 
Independent: RETI vs TF-CBTDependent: Child measured outcomes (CPSS-V (child and CG, SMFQ (child and CG))

		
 • Nesting: student under provider, time • Mediator: BASIS Mechanism (provider-level data) 
** There will be four different models- 1) base model with only intercept, 2) model with only IV, DV, and time, 3) model with IV, DV, time, and TF-CBT vs RETI interaction with time, and 4) lastly, IV, DV, and study group interaction (BASIS, AC, RETI) with time.

	Aim 1c: Evaluate the cost and cost-effectiveness of TF-CBT for improving clinical outcomes	

Main aim	Sub aim	Analysis method
Aim 2: Experimentally evaluate the impact of BASIS versus Attention Control (AC).	Aim 2a: Evaluate main effects on proximal implementation mechanisms of change (attitudes, subjective norms, self-efficacy, intentions to implement, and maintenance self-efficacy).	
Multilevel model
 
 • Independent (IV): AC vs BASIS • Dependent (DV): attitudes, subjective norms, self-efficacy, intentions • Nesting: Piecewise time (training, active, sustainment) • Interaction: Time X Study group 
 ◦ T1 to T5 X BASIS ◦ T6 to T9 X BASIS ◦ T10 to T12 X BASIS 
** There will be four different models- 1) model with only intercept, 2) model with only IV, DV, and time, 3) model with IV, DV, and study group interaction (BASIS, AC) with time, 4) 3) lastly, model with IV, DV, and study group interaction (BASIS, AC, and RETI) with time.

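### Aim 2a starts at T1, a post-randomisation survey, and leaves out the pre-randomisation Provider Baseline; this matters mainly for the BASIS, AC and RETI model

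*Combined protocol and SAP*

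**What the plan says.** Section Two, 1.2 (Pre-Training Activities) gives a dated task list, and its earliest block must be worked through in order.

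- Two to four months before training: "Send Provider Baseline, give 1-2 weeks for completion", and after that "Randomize Providers based on baseline and demographics information".
- One month before: "Send Self-Paced Training link for those who are in TF-CBT".
- One week before: "T1 sent for completion". Course completion is still being chased on the Friday before training, and anyone who has not answered T1 does so in the first five minutes of training.

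Section Two, 1 (Conditions Overview), under TF-CBT, requires providers to "complete TF-CBT online training (providers will be compensated) a week prior to participating in a standard 2-day training".

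Section Two, Randomization, says what the baseline holds and how it was used: "We collected baseline provider data on implementation intentions and TPB and HAPA mechanisms (e.g., attitudes, norms, self-efficacy), identify matched pairs using these variables". Schools were first blocked by state and district. Providers are blinded to BASIS condition.

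Section Four, 1 (Provider Measures) schedules twelve surveys, T1 to T12. The Provider Baseline is not among them.

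Section Six, Aim 2a, analyses attitudes, subjective norms, self-efficacy and intentions in a multilevel model with piecewise time. The first interaction segment is "T1 to T5 X BASIS", followed by T6 to T9 and T10 to T12. The last model in the list compares BASIS, AC and RETI over time. No baseline covariate, pair term or block term appears.

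**The concern.** A randomised comparison of change needs a starting value that assignment cannot have affected. The Provider Baseline is such a value. T1 is not, because it follows both assignment and the release of a course that RETI providers are not sent.

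In the three-group model, a shift in the TF-CBT arms before T1, whether from the course or from knowing one is in a TF-CBT arm, becomes part of the group difference in starting level. The model then cannot tell it from chance imbalance, and the training-phase time-by-group effect excludes it. The estimate describes change after T1, not the effect of being assigned to TF-CBT rather than RETI.

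Two lesser costs apply to Aim 2a as a whole. The analysis ignores variables on which the design was balanced. And a provider who left between randomisation and T1 contributes no outcome value, although a pre-randomisation value was collected.

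**Working it through.** The documents give no power, sample-size or variance figure for Aim 2a, so there is no stated number to reproduce. The check is of timing first, then of scale.

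**1. Order of events (Section Two, 1.2 and Randomization).** Provider Baseline → randomisation (both 2–4 months before training) → course link to TF-CBT arms (1 month before) → T1 (from 1 week before up to the first five minutes of training) → T2 onward. The Provider Baseline cannot be T1 under another name, since the list has both, on opposite sides of randomisation.

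**2. What the three-group model loses.** Let d1 be the mean shift in the TF-CBT arms relative to RETI by T1, and d5 the shift by T5, both measured from the Provider Baseline. The randomised effect at T5 is d5. The T1-to-T5 time-by-group effect is d5 − d1, so d1 is lost. Neither its size nor its sign can be taken from the documents. One detail adds weight: after training the task list sends T2 to TF-CBT providers and T5 to RETI providers. If RETI providers skip T2 to T4, which this suggests but does not state, T1 is the only earlier point for the RETI training-phase slope.

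**3. Precision, BASIS versus AC.** Assume a common correlation r between all occasions (not given in the documents) and unit variance. The relative variance of a later-wave contrast is

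- adjusted for T1 only: 1 − r²
- adjusted for T1 and Provider Baseline: 1 − 2r²/(1 + r)

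| r (assumed) | T1 only | T1 + baseline | Ratio | Reduction |
|---|---|---|---|---|
| 0.3 | 0.910 | 0.862 | 0.947 | about 5% |
| 0.5 | 0.750 | 0.667 | 0.889 | about 11% |
| 0.7 | 0.510 | 0.424 | 0.830 | about 17% |

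**4. Precision of a pure slope term.** Assume balanced data, a provider random intercept, five equally spaced waves (times −2 to 2, sum of squares 10) and, for illustration, 50 providers per arm. The variance of the slope difference is 2(1 − r)/(50 × 10) = 2(1 − r)/500. This gives 0.0020, 0.0016 and 0.0012 at r = 0.5, 0.6 and 0.7, with or without a baseline main effect, because the random intercept already absorbs stable differences between providers. Adding the baseline only as a main-effect covariate therefore does nothing for this term.

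**5. Early loss.** Section Three reports 191 providers randomised and 146 completing training: 191 − 146 = 45, and 45/191 = 23.6%, over all three arms. How many of the 45 left before T1 is not given.

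**The case against.** The strongest reply is that Aim 2 asks about BASIS versus AC, and T1 serves that question reasonably well. Both arms take the same course, providers are blinded to which of the two they are in, and T1 appears to precede the BASIS and AC sessions. It is also closer in time to the outcomes than a survey sent months before. This stands, with one reservation: the documents never say outright that T1 comes before those sessions, and T1 may be answered as late as the opening minutes of training.

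A second reply is that exposure before T1 is not certain. Completion a week ahead is required, yet it is still chased after T1 has gone out, so some providers may answer T1 first. That stands too: completion before T1 is planned, not guaranteed. The TF-CBT description also words the course requirement as if it covered every school provider. However, it does so within the account of TF-CBT, and the task list limits the link to the TF-CBT arms.

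A third reply concerns the remedy. The document is dated 3/5/2025 and already reports a fidelity finding under Aim 2b, so a new covariate may be post hoc. Matched pairs are not clearly defined when there are three conditions and assignment is described at both school and provider level, and attrition may have broken some pairs. The baseline instruments are not listed in Section Four, so identical scales cannot be assumed. These points limit how the fix is made. They do not remove the need for it.

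A reader might infer that baseline adjustment would cut variance by r², or 25% to 49% at r = 0.5 to 0.7. That compares adjustment with no earlier measure at all, whereas this model already contains T1.

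**Conclusion.** The point holds, with modest severity. T1 is post-randomisation, the Provider Baseline is unused in Aim 2a, and in the BASIS, AC and RETI model T1 is not an equivalent starting point. The resulting distortion of the training-phase effect equals whatever shift occurred in the TF-CBT arms before T1, and it cannot be sized from the documents.

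For BASIS versus AC the cost is mainly precision: roughly 5% to 17% of variance for a T1-adjusted contrast, assuming equal correlations of 0.3 to 0.7, and nothing for a pure slope term under balance and a random intercept. There are also no outcome data for whichever of the 45 lost providers left before T1.

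A reader might infer that the BASIS versus AC result is biased, or that all 45 lost providers are missing from the model. The documents support neither: the two arms share the course and the blinding, and the number leaving before T1 is not stated. Nor are the main analyses directly affected, since Section Six names these as Aims 1b and 2b. Aim 2a still matters because the Aim 2b mediation relies on the same mechanisms.

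**What to change.** In Section Six, Aim 2a:

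- Where the Provider Baseline measured the same construct, enter that score as the pre-randomisation occasion with arm means constrained equal. Alternatively, contrast each later wave with it, adjusting for it.
- In the three-group model, treat T1 as a post-randomisation wave and report the arm difference at T1.
- Include the state and district block and the matching variables. Use pair terms only where pairs are defined and intact.
- State which instruments the Provider Baseline used, when T1 falls relative to the course and to the BASIS and AC sessions, and how many providers left before T1, by arm.
- Optionally, add baseline intention to the Aim 2b adoption analysis; no calculation here supports more than that.

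The baseline data were needed for matching, so no new collection is required. The cost is SAP wording and some extra analysis. If Aim 2a results have already been seen, the new model must be labelled as added later and shown beside the T1-start model.
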